#### 3. Abstract:

Locomotor training is a well-established rehabilitation strategy that promotes walking recovery after ISCI. A primary objective of this approach is to promote recovery of spinal locomotor circuitry through excitation from descending motor signals and afferent somatosensory inputs to the spinal cord. 5,6 Following locomotor training, individuals with ISCI often demonstrate improved walking function. 1,3,7,8 However, most people with ISCI continue to have serious walking impairments that limit mobility, community participation and quality of life. A key limitation of current rehabilitation approaches, including locomotor training, is insufficient excitation of spinal locomotor circuitries. 6,10,11 Excitation is needed to drive neuroplastic recovery. Since the majority of SCIs are incomplete, a promising strategy to promote spinal excitation is to use adjuvant approaches that leverage spared pathways and the intact afferent pathways below the level of the lesion. 5,12,13 Transcutaneous spinal direct current stimulation (tsDCS) is a neuromodulatory approach that uses mild and non-invasive electrical stimulation. 14,15 tsDCS induces immediate and lasting changes in spinal cord excitability 14,16-18 and alters reflexive and voluntary behaviors in rodents. 19 Likewise, in humans, tsDCS modulates spinal reflexes, increases corticospinal excitability, and increases motor unit recruitment. Although ample mechanistic evidence suggests that tsDCS could substantially enhance the therapeutic effect of locomotor rehabilitation, this combinatorial approach has not been evaluated in humans with SCI. We propose a proof-of-concept study to investigate the effects of tsDCS on locomotor function and rehabilitation outcomes in individuals with ISCI. The immediate effects of tsDCS will be examined by testing changes in muscle activation, walking kinematics and spinal reflex excitability after a single period of tsDCS application. Furthermore, we will test the hypothesis that tsDCS applied during a regimen of locomotor training will improve the functional walking

outcomes achieved. Results of this pilot project may contribute to the development of a combinatorial rehabilitation strategy that leverages current best practice and a novel non-invasive neuromodulation approach to enhance recovery of walking after ISCI.

# 4. Background:

Locomotor training is a well-established rehabilitation strategy that promotes walking recovery after ISCI. 1-3,7-9,23-27 Locomotor training emphasizes repetitive and task-specific practice of coordinated walking, often with therapist assistance or cueing to promote high quality movement patterns. A primary objective of this therapy is to promote neuroplastic recovery of spinal locomotor circuitry through excitation from descending motor signals and afferent somatosensory inputs to the spinal cord. 5,28 Somatosensory inputs include limb loading and hip extension, which are known to elicit afferent volleys that are important for facilitating propulsion and swing initiation, respectively. 29-34 Following locomotor training, individuals with ISCI often demonstrate improved walking function. 1-3,7-9,23-27 However, most people with ISCI continue to have serious walking impairments that limit mobility, community participation and quality of life. 1-3,7,9 Adjuvants that increase spinal excitation during locomotor training may enhance the effectiveness of this therapy. 6,35

A key limitation of current rehabilitation approaches is insufficient excitation of spinal locomotor circuitries. Excitation is necessary to drive Hebbian learning and activity-dependent neuroplasticity. Since the majority of spinal cord injuries are incomplete, a promising strategy for promoting excitation of the spinal cord is to use adjuvant/combinatorial approaches that leverage spared pathways and the intact afferent pathways below the level of the lesion. 13,28,35 Here we propose to combine transcutaneous spinal direct current stimulation (tsDCS) with locomotor training to increase spinal excitation and thereby increase the effectiveness of locomotor rehabilitation. tsDCS is a neuromodulation approach that uses a mild electrical current to alter the membrane potential of spinal neurons. 18,36 We propose to use an electrode montage that has been shown to induce a net depolarization, thereby bringing neurons closer to their discharge threshold. 21,22 When applied during walking, this increased excitability of spinal neurons contributes to a physiological environment that is more responsive to task-specific activation by descending/motor and afferent/somatosensory pathways. This combinatorial strategy is particularly promising because tsDCS is a relatively simple, non-invasive approach that realistically could be implemented in clinical settings. Overall, accumulating evidence indicates that a combined tsDCS strategy is likely to be effective and is a critical next step in advancing neuromodulation for locomotor rehabilitation.

tsDCS modulates spinal reflexes and locomotor circuits. tsDCS involves the delivery of a mild constant direct current over the spinal cord through surface electrodes. This approach is noninvasive, relatively simple and well tolerated. tsDCS can induce immediate and lasting changes in spinal cord excitability 16,38,39 and can alter reflexive and voluntary behaviors in rodents. 19 During locomotion, tsDCS has been shown to modulate both alpha and gamma motor neuron activity and improve rhythmic motor output. 19 Specifically, tsDCS has been reported to modulate somatosensory input and improve the coordination and amplitude of muscle activation during treadmill locomotion. 19 Human

data indicate that tsDCS increases corticospinal excitability and motor unit recruitment.

tsDCS also modulates spinal reflexes in humans  which may be beneficial for improving walking function after ISCI.  After ISCI, spinal reflexes are altered and poor reflex modulation contributes to walking impairments.  For instance, reflex hyper-excitability and reduced post-activation depression of the Hoffman reflex (H-reflex) contributes to over-activation of the ankle plantarflexors during walking.  tsDCS has been shown to increase post-activation depression in heathy individuals,  suggesting tsDCS could have a beneficial effect on walking function in adults post SCI. These effects may be even greater when combined with walking rehabilitation since walking rehabilitation is also known to modulate spinal reflexes by increasing post-activation depression  and improving reflex modulation during walking. 

Overall, studies of tsDCS support its use as a neuromodulatory approach. The next important step is to test whether this approach can substantially augment the effectiveness of locomotor rehabilitation and improve the neuromuscular control of walking in individuals with ISCI and other neurological conditions. Also noteworthy is that the potential efficacy of tsDCS is supported by a parallel body of evidence from direct current brain stimulation, which shows gains in motor and cognitive function for neurologically-impaired populations such as adults post-stroke.

## 5. Specific Aims:

Specific Aim 1 (Cross-sectional): To test the hypothesis that tsDCS applied during walking will improve muscle activation and lower limb kinematics in adults with chronic ISCI. A random order, double blind cross-over study will be conducted across two test sessions to compare the immediate effects of two dosages of tsDCS during walking. The higher dosage of tsDCS aligns with previous research protocols, while the lower dosage can be effectively be viewed as sham stimulation. Bilateral lower extremity surface electromyograms and 3-dimensional kinematics will be recorded. Outcomes will be changes in muscle activation amplitude and timing, and hip joint excursion during walking. tsDCS induced changes in spinal excitability, as measured by tests of the Hoffman reflex (H-reflex), also will be assessed.

Specific Aim 2 (Interventional): To test the hypothesis that tsDCS applied during 16 sessions of locomotor training will improve functional walking outcomes. Participants will be randomized to receive 16 sessions of tsDCS at one of the two dosages with locomotor training. Primary functional outcomes will include standardized clinical tests of walking speed and endurance. Secondary outcomes will include quantifying changes in muscle activation amplitude and timing, lower limb kinematics and the cortical control of walking during over ground walking.

#### 6. Research Plan:

#### Recruitment

A minimum of eight individuals are required to complete this pilot study. We aim to screen 30 individuals and enroll 20 subjects in this study. The target population will be

individuals with SCI. Study procedures will take place at Brooks Rehabilitation, which includes a clinical research facility directed by [name] (Principal Investigator). Potential participants will learn about the study and be recruited in the following primary ways:

- Local advertisements or study flyers (see Recruitment Methods attachments
  for study flyer and email script for potential participants). Individuals may
  contact study personnel at Brooks Rehabilitation. Study staff will be available
  to answer any questions and if the potential participant is interested, the
  individual will be screened for eligibility (screening process detailed below).
- 2. Health care providers at Brooks Rehabilitation or other clinics in the north Florida area (e.g. physicians, physical therapists, or occupational therapists) (see Recruitment Methods attachments for email script for healthcare providers). Health care providers may ask potential participants if they would like to learn more about a current research study. If interested, the potential participants will be provided with a flyer, which will contain instructions for contacting the study staff at the Brooks Rehabilitation Motion Analysis Center. Study staff will be available to answer any questions and if the potential participant is interested, the individual will be screened for eligibility.
- 3. Additionally, the health care provider may ask the potential participant if they are interested in being contacted by a study staff member regarding this research study (see Recruitment Methods attachments for authorization to release patient information form). If written authorization is provided by the potential participant, the health care provider will request his/her name, telephone number, and email address in order to be contacted by the study staff directly. This recruitment strategy will be necessary to help facilitate communication between the potential participant and the study staff. Study staff will contact the potential participant and answer any questions. If the potential participant is interested, the individual will be screened for eligibility.
- 4. Individuals admitted to Brooks Health System. All individuals admitted to Brooks Health System sign a Brooks Notice of Privacy Practices upon admission which indicates their information may be used for research (see Recruitment Methods section attachments for Brooks Notice of Privacy Practices). This is a standard practice for the Brooks Health System facilities. We have attached this form to the Recruitment Methods section. For individuals who sign this form, Brooks Research Recruitment personnel have permission to access their medical records for research-related purposes. Therefore, Brooks Research Recruitment personnel would be aware of our study (as it is being conducted at a Brooks facility) and would include this as one of several potential research study opportunities when contacting Brooks patients. This procedure is independent of our research study procedures and is carried out by Brooks Research Recruitment personnel; potential participants will only be contacted for screening for this specific study if they indicate to Brooks Research Recruitment personnel that they want to learn more about our study.

# Screening and Enrollment

Individuals who are interested in participating in the study will be asked to complete a three-step screening process to determine if they are eligible to participate. **Informed consent will be obtained twice-** once during screening and, if enrolled for the full study, a second time for the study procedures. Individuals will have ample opportunities to ask questions about the study prior to enrollment.

The screening procedures will verify the participant meets the following inclusion and exclusion criteria:

#### Inclusion criteria

- 1) Male or female, ages 18-65
- 2) Single spinal cord injury (duration >1 year) classified as neurologic level T12 or above based on the International Standards for the Neurologic Classification of Spinal Cord Injury, and classified on the American Spinal Cord Injury Association (ASIA) Impairment Scale (AIS) as 'C' or 'D' motor incomplete
- 3) Capable of ambulating 10 feet with or without the use of gait devices, braces, or the assistance of one person
- 4) Medically stable with no acute illness or infection
- 5) Able to provide informed consent

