## Study Procedures Overview

For Aim 1 (immediate effects of tsDCS), participants will complete two separate testing sessions, presented in random order, that involve up to 30 minutes of tsDCS at one of the two dosages while walking. We will assess changes in muscle activity, kinematics and spinal excitability before and at the end of the period of walking. The two sessions will last about 3 hours and no longer than 6 hours and will take place at least 48 hours apart to allow for wash-out of stimulation effects.

For Aim 2 (effects of tsDCS applied with locomotor training), participants will be randomized to receive 16 sessions of locomotor training with tsDCS at one of the two dosages. Each intervention session will last about 1 hour and no longer than 2.5 hours. Before and after the 16-session intervention (i.e., at baseline and post intervention), we will assess functional outcomes through standardized clinical tests of walking speed and endurance, as well as changes in muscle activity, kinematics and spinal excitability. We will also examine the participant's spasticity and pain using standardized assessments. Each assessment session will last about 3 hours and no longer than 6 hours.

Overall, the testing and intervention procedures of this study will be as follows (see Fig. 1 for details):

- 1. Aim 1's first visit will consist of clinical testing and collection of basic demographic information (see Information Sources and Identifier attachments for demographics form) to characterize the participant. Neuromechanical assessments of walking and reflex testing prior to and after 30 minutes of tsDCS at one of the two dosages delivered while walking on a treadmill will be conducted.
- 2. Aim 1's second visit will involve identical procedures for stimulation and neuromechanical assessments as compared to visit 1 except for crossover of the tsDCS dosage. It will also include any clinical testing not completed on day 1.
- 3. Aim 2's pre-test will consist of neuromechanical assessments of walking and reflex testing as well as clinical assessments of pain, spasticity, and physical function.
- 4. 16 sessions of locomotor training will be conducted over 4 weeks with one of the two dosages of tsDCS applied during the training.
- 5. Aim 2's post-test will repeat the measures completed at pre-test.

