A physical therapist will oversee study procedures. Vital signs, such as blood pressure, heart rate and blood oxygen saturation, will be monitored for safety. Rest breaks will be provided at regular intervals and at any time the participant requests. Participants will be informed that they may choose not to perform any aspect of the study. We will adjust the assessment protocol, outlined below, as needed in response to our participants, such as reducing the assessments due to fatigue or individual tolerance.

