- Measurement of joint motions during standing and walking- To quantify trunk and lower extremity joint motions, a 12-camera three-dimensional motion analysis system will be used to collect marker data and measure joint kinematics during walking tasks. Small, lightweight reflective markers will be placed on the upper and lower extremities and the trunk using an established marker set. To reduce artifact and improve accuracy of motion analysis data, reflective markers will be placed directly on the skin when possible using hypoallergenic double-sided tape. Individuals will be asked to wear tight, minimal clothing, such as tank tops and athletic shorts, to provide access to bony, anatomical landmarks as able.
- Recording of muscle activation- A wireless, 16-channel surface electromyography (EMG) system will be used to record muscle activation during the standing and walking activities. In the small area over the muscle where the sensors will be placed, the skin will be shaved and cleaned with alcohol prior to attaching the sensors with hypoallergenic double-sided tape. These procedures optimize EMG signals by reducing noise and impedance. EMG signals will be recorded using the motion capture software to synchronize collection of the EMGs and motion data (kinematics).
- Assessment of kinetics and spatio-temporal movement characteristics-Ground reaction forces (kinetics) will be recorded during the walking activities. The participants will be asked to walk over the standard built-in force plates, which are flush with the floor and are not an obstacle or tripping hazard. This will be done while they also are wearing the EMGs and reflective markers so that all data are captured simultaneously. During the session, the participant may be asked to stand or walk over a 12' instrumented walkway (i.e. GaitRite). The walkway appears like a flat, carpeted surface and has embedded sensors to record foot falls and foot placement. The edges of the walkway will be taped down to be nearly flush with the floor and to minimize the possibility of tripping. Participants will be guarded at all times and/or an overhead harness may be

used. The instrumented walkway will provide quantitative data regarding the spatial and temporal characteristics of standing and walking.

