## Delivery of tsDCS

tsDCS will be delivered to the low back, over the lumbar region of the spinal cord, using a commercially available direct current stimulation unit (Soterix Medical Inc). Each tsDCS electrode is comprised of a carbon rubber electrode encased in a saline-soaked sponge. The electrodes will be placed on the participant using a previously established configuration to target the lumbosacral cord with two electrodes on the abdomen placed

to the left and right of the umbilicus and one over the lumbar spinal cord at the level of the 11th and 12th thoracic vertebrae. A large elastic bandage with Velcro closure will be wrapped around the abdomen to hold the electrodes firmly in place. Participants will be closely monitored for any adverse responses such as skin irritation and pain. This electrode configuration has been shown to appropriately target the lumbosacral spinal cord, as validated

by modeling of electrical current flow and by gains in lower extremity motor performance. A low dosage of ≤ 2.5 mA stimulus will be used for the "higher" dosage. This dosage (or very similar) has been used in numerous prior studies and has been shown to be well-tolerated and to produce measurable changes in reflex activity and/or lower extremity motor performance. An identical montage and stimulation arrangement will be used for the "lower" dosage, except the stimulation will be delivered in a brief ramp-like manner for 30 seconds at the beginning and end of the stimulation period. The "lower" dosage condition is effectively a "sham" procedure. This approach is widely used in the field of direct current stimulation, and has been reported to be indistinguishable from the "higher" dosage protocol. This is because participants quickly habituate to the sensation of active stimulation. To assess the effectiveness of our low dose/sham stimulation, participants will be asked during Aim 2 post-testing which

dosage they believe they received and how certain they are of their opinion. They will then be informed which dosage they received.

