## Statistical Plan

A descriptive analysis of demographic data and injury characteristics will be conducted using a frequency distribution for categorical data and means for continuous variables. These data will be used to characterize general information about the study population. Sample size and data distribution will guide statistical analysis. If data assumptions are achieved, for Aim 1, we will determine the effects of tsDCS during walking using two-way repeated measures ANOVAs. The within factors will be time (before or at the end of walking bout) and stimulation (higher or lower dosage tsDCS). We will then examine the interaction effect to determine differences in the changes during walking with the two dosages of tsDCS. For Aim 2, mixed method ANOVAs will be used to determine the effects of tsDCS dosage during locomotor training. The within factor will be time (pre- or post-test) and between factor will be group (higher or lower dosage tsDCS). We will then examine the interaction effect to determine differences in the improvement during locomotor training with the two dosages of tsDCS. Differences will be considered significant at p<.05. Data will be analyzed using professional statistical software.

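### Does a 10-foot entry walk, with no scoring rule for an unfinished 10-metre walk test, undermine the Aim 2 walking-speed comparison?

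*Combined protocol and SAP*

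**What the plan says.** - **Entry (Inclusion criteria).** A participant must be "Capable of ambulating 10 feet with or without the use of gait devices, braces, or the assistance of one person". The paragraph closing the Exclusion criteria lets the investigator exclude anyone whose ability to carry out the procedures is in doubt. It also allows a small shortfall, with 8 feet as its example, for someone who shows they can get through testing and training.
- **Outcome (Specific Aims; Clinical assessments).** Aim 2's primary outcomes are clinical tests of walking speed and endurance. The 10-Meter Walk Test (10MWT) is the only forward-speed test on the clinical list; the 3-metre test is backward. The 6-Minute Walk Test covers endurance.
- **Earlier sight of the 10MWT.** Step two of screening lists the 10MWT among tests that may be used, whole or in part, to confirm eligibility. Aim 1 uses the clinical assessments to characterise participants, and of its second visit the Study Procedures Overview says "It will also include any clinical testing not completed on day 1".
- **Flexibility (Study Procedures Overview).** Participants are told "they may choose not to perform any aspect of the study", and staff may adapt the protocol, "such as reducing the assessments due to fatigue or individual tolerance".
- **Analysis (Statistical Plan).** "Sample size and data distribution will guide statistical analysis". Aim 2 then uses a mixed ANOVA with time and dosage group, read through the interaction. There is no rule for an unfinished test.
- **Disclosure (Delivery of tsDCS).** To check the sham, "participants will be asked during Aim 2 post-testing which" dosage they think they had. "They will then be informed which dosage they received".

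**The concern.** Someone can satisfy the written entry criterion having shown less than a third of the distance in the primary speed test. If that person starts the 10MWT and stops, the analyst has three reasonable options: leave the person out, record 0 m/s, or divide the distance covered by the time taken. These can give different changes from pre-test to post-test.

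The plan says the analysis will be guided by the data, and dosage is disclosed to participants at post-testing. So nothing in the text forces the option to be chosen before results or allocation are known. With as few as eight completers, one person carries a lot of weight. At stake would be a dosage difference that depends on a choice made after the fact, and a false-positive rate above the nominal 5%.

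**Working it through.** The plan gives no effect size, standard deviation or power figure, so there is no figure of its own to reproduce.

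**1. Distances.**
- Entry: 10 ft × 0.3048 = 3.05 m, and 10 / 3.048 = 3.28.
- The 8-foot example: 8 × 0.3048 = 2.44 m, or 24.4% of 10 m.
- The optional walkway in Neuromechanical assessments of walking ("the participant may be asked to stand or walk over a 12' instrumented walkway"): 12 × 0.3048 = 3.66 m, or 1.2 times the entry distance.

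The mismatch is a fact. Ten feet is a minimum, however, and the documents do not say how many entrants would be near it.

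**2. Precision lost if one person is omitted.** With two visits, the group-by-time interaction is the same test as a two-sample t-test on change. The 95% interval half-width is proportional to t(0.975, n1+n2−2) × √(1/n1 + 1/n2). The Recruitment section gives 8 completers as the minimum and 20 as the enrolment target; equal arms are assumed.

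| Arms | t × root | Product | Ratio |
|---|---|---|---|
| 4+4 | 2.447 × 0.7071 | 1.730 | |
| 4+3 | 2.571 × 0.7638 | 1.964 | 1.135 |
| 10+10 | 2.101 × 0.4472 | 0.940 | |
| 10+9 | 2.110 × 0.4595 | 0.970 | 1.032 |

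The interval widens by 13.5% or 3.2%. That is a cost in precision. Omitting people who could not finish the pre-test, which precedes the intervention, does not by itself bias the dosage comparison.

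**3. How far one person moves the estimate.** Assume everyone gains 0.10 m/s except one higher-dosage participant who covers 9 m and then the full 10 m, both at 0.25 m/s.

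| Rule | 4 per arm | 10 per arm |
|---|---|---|
| Omit | 0.30/3 − 0.10 = 0 | 0.90/9 − 0.10 = 0 |
| Score 0 m/s | (0.30 + 0.25)/4 − 0.10 = +0.0375 | (0.90 + 0.25)/10 − 0.10 = +0.015 |
| Distance/time | (0.30 + 0)/4 − 0.10 = −0.025 | 0.90/10 − 0.10 = −0.010 |

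The sign changes only because everyone else was given an identical gain, so any departure sets the sign. Now let change have an assumed standard deviation of 0.10 m/s:
- 4 per arm: half-width 1.730 × 0.10 = 0.173 m/s; largest shift 0.0375 / 0.173 = 22%.
- 10 per arm: half-width 0.940 × 0.10 = 0.094 m/s; largest shift 0.015 / 0.094 = 16%.

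**4. False-positive rate.** Simulation with no dosage effect, 100,000 trials per setting. Assumptions: change normal with mean 0.10 and SD 0.10 m/s in both arms; 5% to 30% unable to finish at pre-test; their baseline speed uniform on 0.1 to 0.4 m/s; half of them finish at post-test.

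| Pre-test non-completers | 5% | 10% | 20% | 30% |
|---|---|---|---|---|
| Best of three rules, 4 per arm | 6.3% | 7.5% | 9.0% | 9.9% |
| Best of three rules, 10 per arm | 6.9% | 8.0% | 9.6% | 10.6% |

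Any single rule, used throughout, gives 4.3% to 5.1%. The excess therefore comes only from running all three and keeping the most favourable, not from the absence of a stated rule.

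**The case for a change.** The best case for acting is that the repair is small and the opening is real. The screening 10MWT is optional and may be partial, and neither investigator discretion nor Aim 1 testing sets a 10-metre threshold. The analysis is openly data-guided, results are tested at p<.05, and double blinding is stated only for Aim 1. Taking the best of three rules can roughly double the error rate, and being a pilot does not excuse that.

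The facts in this argument stand; the inference is weaker. The inflated rates describe an analyst who shops among rules, and the plan does not provide for that. A general remark that sample size and distribution will guide the analysis reads naturally as a check of ANOVA assumptions, which is how the following sentences of the Statistical Plan use it. The disclosure step concerns the participant, not whoever scores the test. Because it follows a question about which dosage was received, sensible staff would take it after the outcome tests. Declined or shortened assessments affect every outcome and are not particular to the 10-foot criterion.

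One caveat survives. If failure to finish at post-test differed by dosage, omission could bias the comparison. That would show in a simple count of non-completers by arm, and nothing in the documents suggests it is expected.

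**Conclusion.** No change follows. This is a missing detail that a competent analyst fills sensibly: the plan does not score an unfinished 10MWT, but any of the three obvious rules, applied alike at both visits, gives a sound test of the dosage comparison. No one rule is shown to be right, so there is no error to correct. The effect is small beside the pilot's own imprecision: at most about 22% of the interval half-width with 4 per arm and 16% with 10 per arm, for one affected person.

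The other primary measure, the 6-Minute Walk Test, has no distance to complete and so is not exposed to this problem.

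The conclusion rests on assumed speeds, gains, a standard deviation of 0.10 m/s, equal arms and 5% to 30% non-completion, none of which is in the documents. It also assumes that one rule is used throughout and that post-test completion does not differ materially by dosage.
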